4.1.1. Duration of Treatment

Subjects will be permitted to remain on study treatment until disease progression per RECIST v1.1, unacceptable toxicity, or other criteria for withdrawal are met (see [Section 7.1](#), whichever occurs first. Subjects who discontinue treatment will return to the clinical site for an EOT visit within 30 days after last dose of study treatment. Subjects who are benefitting from

study treatment at the time of the EOS may continue treatment in the Extended-Use phase of the study.

4.1.2. Long-Term Follow-Up Period

For subjects in the main study who discontinue treatment and do not withdraw consent, there will be a LTFU period for clinical evaluation of disease status and survival. Survival follow up will be discontinued for subjects currently in LTFU at the time of the initiation of the Extended-Use phase. See [Section 7.2](#) for details.

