Cycle/Day	Screening ¹		Treatment							EOT/ EOS ²	LTFU ³³	Extended -Use ³⁴	Extended -Use EOT/ EOS ²
			Cycle 1 (21-Days)		Cycle 2 (21-Days)		Cycle 3 (21-Days)	D1 of Every Cycle (After C3)	D1 of Every Other Cycle (After C3)				
Day	-28 to 1	-14 to 1	1	8 (±1D)	15 (±1D)	1 (±1D)	15 (±1D)	1 (±1D)	1 (±1D)	(+30D)	(±14D)	After Main EOS	(+30D)
Pregnancy Test (FSH and Estradiol, if needed) ²⁴		X	X			X		X	X	X			X
Hepatitis B and C Virus Tests ²⁵	X												
CPK (Total and MM Isoenzymes) ²⁶			X		X	X		X	X	X			
CT Scan ²⁷	X							X (±1 week)		X			
Brain MRI ²⁸	X												
RECIST v1.1 Tumor Response Assessment ²⁹								X (±1 week)		X			X
Study Treatment Administration													
RMC-4630 ³⁰			<-----	----->								X	
Sotorasib ³¹			<-----	----->								X	
Dosed QD----->													

Table 1: Schedule of Activities for Protocol RMC-4630-03 (Continued)

Cycle/Day	Screening ¹	Treatment							EOT/ EOS ²	LTFU ³³	Extended -Use EOT/ EOS ²	Extended - Use EOT/ EOS ²	
		Cycle 1 (21-Days)		Cycle 2 (21-Days)		Cycle 3 (21-Days)	D1 of Every Cycle (After C3)	D1 of Every Other Cycle (After C3)					
Day	-28 to 1	-14 to 1	1 (±1D)	8 (±1D)	15 (±1D)	1 (±1D)	15 (±1D)	1 (±1D)	1 (±1D)	(+30D)	(±14D)	After Main EOS	(+30D)
PK and Biomarker Assessment													
PK Sampling ³²			See Table 2										
Blood for ctDNA biomarker ³³			See Table 2							X			
Archival tumor tissue (FFPE) for solid tumors or fresh-tissue biopsy ³⁴	X												
Long-Term Follow-up													
Telephone contact for survival status ³			Only completed after EOT								X		

¹ Screening window is 14 days, unless otherwise specified. Informed consent and subject demographics, medical history, smoking status, documentation of tumor genotypic mutations, screening hepatitis tests, CT/MRI scan, ECHO/MUGA, and ophthalmic examination may be obtained 28 days before C1D1.

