² Subjects who discontinue study treatment should complete the EOT visit within 30 days of last dose of study treatment. Subjects who wish to withdraw from treatment should be encouraged to complete the EOT assessments. If a subject chooses to withdraw from the study completely, record the reason for withdrawal on the appropriate page(s) of the eCRF. Subjects who are on treatment at the main EOS and are deriving clinical benefit from RMC 4630 and sotorasib will be considered for enrollment in a separate Extended-Use phase. These subjects should enter the Extended-Use phase without interruption of treatment and should complete main EOT assessments to receive treatment on Day 1 of the Extended-Use phase. EOT/EOS for the Extended-Use phase will be performed within 30 days of the last dose in the Extended-Use phase.

³ After termination of treatment, subjects in the main study will remain on study for survival follow-up. Survival follow up will be discontinued for subjects currently in LTFU at the time of the initiation of the Extended-Use phase.

⁴ Assessments performed during the Extended-Use phase will occur as clinically indicated, unless specified otherwise.

⁵ Obtain written informed consent from the subjects before any protocol required procedures and assessments are performed. Standard of care evaluations performed as part of the subject's routine treatment prior to signing consent may be used if they were done in the timeframe required for screening.

⁶ Demographic information includes the following: age, gender, race, and ethnicity.

⁷ Prior cancer history includes: (i) date of diagnosis, (ii) staging, (iii) all previous therapies (ie, chemotherapy, immunotherapy, biologic or targeted agents, experimental therapies, radiotherapy, and surgery), (iv) previous therapy details (ie, regimen, start and stop dates), (v) best response for each regimen, (vi) date of relapse or disease progression, and (vii) any molecular characterization of tumor (eg, PD-L1 expression).

⁸ Documentation of KRASG12 NSCLC in a prior genomic report within 3 years of study enrollment. Please see [Appendix 9](#) for a detailed list of genetic aberrations, which may be allowed for subjects enrolling in Cohort 2 of the dose expansion portion of the study.

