8.1. Efficacy Assessments

Subjects will be assessed for response using RECIST v1.1 (see [Appendix 6](#)), as assessed by the investigator. All measurable disease must be documented at screening and reassessed at each subsequent tumor evaluation. Measurable disease is required for each subject (Inclusion Criterion 3 [[Section 5.1](#)]). Response assessments will be assessed by the investigator based on physical examination (including measurement of cutaneous lesions) and CT scans or MRI. Imaging should include chest and abdomen (depending on primary tumor type, site of metastasis and investigator assessment). At the investigator's discretion, the imaging studies may be repeated at any time if disease progression is suspected. Additional studies, such as positron emission tomography (PET) or bone scans, should be performed if clinically indicated. Care should be taken to repeat the same modality used at screening throughout the study and to ensure all anatomy imaged at screening is again imaged at follow-up scans for any given subject. As part of the tumor assessment, physical examinations should include all areas of tumor involvement that are amenable to examination, including biopsy sites, lymph nodes, and bone tenderness, if applicable.

All imaging studies should be evaluated by a local radiologist with expertise in the imaging modality. The investigator is responsible for determining the overall response at each timepoint.

Radiological imaging and tumor assessments are required at screening and every 2 cycles starting from Cycle 3 (ie, every 6 weeks [± 1 week]) up to Cycle 9, every 4 cycles (ie, every 12 weeks [± 1 week]) thereafter and EOT. Radiographic response (CR and PR) requires

confirmation by a repeat scan at least 4 weeks after the first documentation of response and may be delayed until the next scheduled scan to avoid unnecessary procedures.

In the Extended-Use phase of the study, tumor imaging is not required per protocol. If required, imaging should be performed according to local standards of care and may be entered in the eCRF at the end of the extended use phase, if available.

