When nodal disease is included in the sum of target lesions and the nodes decrease to “normal” size (<10 mm), they may still have a measurement reported on scans. This measurement should be recorded even though the nodes are normal in order not to overstate progression should it be

based on increase in size of the nodes. As noted earlier, this means that subjects with CR may not have a total sum of “zero” on the CRF.

In trials where confirmation of response is required, repeated “NE” time point assessments may complicate best response determination. The analysis plan for the trial must address how missing data/assessments will be addressed in determination of response and progression. For example, in most trials it is reasonable to consider a subject with timepoint responses of PR-NE-PR as a confirmed response.

Subjects with a global deterioration of health status requiring discontinuation of treatment without objective evidence of disease progression at that time should be reported as “symptomatic deterioration.” Every effort should be made to document objective progression even after discontinuation of treatment. Symptomatic deterioration is not a descriptor of an objective response; it is a reason for stopping study therapy. The objective response status of such subjects is to be determined by evaluation of target and nontarget disease as shown in [Table A6-1](#).

Conditions that define “early progression, early death and un-evaluability” are study specific and should be clearly described in each protocol (depending on treatment duration, treatment periodicity).

In some circumstances, it may be difficult to distinguish residual disease from normal tissue. When the evaluation of complete response depends upon this determination, it is recommended that the residual lesion be investigated (fine-needle aspirate/biopsy) before assigning a status of complete response. FDG-PET may be used to upgrade a response to a CR in a manner similar to a biopsy in cases where a residual radiographic abnormality is thought to represent fibrosis or scarring. The use of FDG-PET in this circumstance should be prospectively described in the protocol and supported by disease specific medical literature for the indication. However, it must be acknowledged that both approaches may lead to false positive CR due to limitations of FDG-PET and biopsy resolution/sensitivity.

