2.2.3 Long-Term Follow-Up Period

For subjects who discontinue treatment and do not withdraw consent, there will be a Lost to Follow-up (LTFU) period for clinical evaluation of disease status and survival. Subjects will be followed via telephone every 3 months (±2 weeks) for assessment of survival and documentation of anticancer treatment. LTFU Subjects will be followed until withdrawal of consent, subject death, or EOS (Protocol Section 4.4), whichever occurs first.

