7.6.2 Secondary Efficacy Analysis

Disease Control Rate (DCR)

DCR is defined as the proportion of subjects who achieve a CR or PR or SD per RECIST v1.1. A CR or PR should be confirmed by a repeat assessment no less than 28 days, and SD requiring the minimum duration of 5 weeks from initiation of first dose of study drug ((i.e., at least 35 days between treatment start and scan date qualifying the subject for a BOR of SD)).

DCR and the corresponding 95% two-sided exact binomial confidence interval using the Clopper-Pearson method will be presented.

Duration of Response (DOR)

DOR is defined as the interval from the first documentation of CR or PR to first documentation of definitive disease progression or death due to any cause, whichever occurs first.

Subjects who are still alive and free from progression at the time of data cutoff date, or lost to follow-up, or discontinued from the study or initiated subsequent anticancer therapy will be censored at the last adequate tumor assessment. Subjects who never achieve a response (PR or better) will be excluded from the analysis of DOR. (Refer to censoring rule document)

$$DOR = (date\ of\ event/censor - first\ date\ of\ confirmed\ CR\ or\ PR + 1) / 30.4375.$$

The Kaplan-Meier method will be used to estimate DOR curves and corresponding quartiles. The Kaplan-Meier median will be calculated with a two-sided 95% confidence intervals. If the number of responders is less than 5, DOR data will be provided in a subject listing.

A Swimmer plot of response and duration of treatment will be presented.

Progression Free Survival (PFS)

PFS is defined as the interval from the first dose of study treatment to documented disease progression per RECIST v1.1 or death due to any cause, whichever occurs first.

For subjects who are still alive and free from progression at the time of data cutoff date, or lost to follow-up, or discontinued from the study, or initiated subsequent anticancer therapy, PFS will be censored at the last adequate tumor assessment.

For subjects with PD or death after two or more missing consecutive scheduled assessments, or if a subject initiated subsequent anticancer therapy before the PD date or death prior to first post-baseline scan, PFS will be censored at the last tumor assessment visit prior to the occurrence of the consecutive missing visits or prior subsequent anticancer therapy respectively.

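### Long-term follow-up is said to cover disease status, but no tumor assessment is scheduled after EOT, so PFS and DOR may be informatively censored for subjects who stop for clinical decline, and the SAP text has no sensitivity analysis for this

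*Protocol*

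**What the plan says.** **Purpose of follow-up.** Protocol 4.1.2: "there will be a LTFU period for clinical evaluation of disease status and survival". SAP 2.2.3 likewise describes a "period for clinical evaluation of disease status and survival".

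**What is collected.**
- In Protocol Table 1 the only activity marked for long-term follow-up (LTFU) is "Telephone contact for survival status". Footnote 3 says: "After termination of treatment, subjects in the main study will remain on study for survival follow-up".
- SAP 2.2.3: "Subjects will be followed via telephone every 3 months (±2 weeks) for assessment of survival and documentation of anticancer treatment".
- Scheduled imaging ends with the EOT scan (Table 1 footnote 27; Protocol 8.1). That scan is waived if progression was already imaged and was the reason for stopping.
- Protocol 7.1 and 7.2 say that subjects in LTFU stop follow-up and that subjects have completed the study once the EOT visit is done. Section 4.1.2 and footnote 3 tie the end of survival follow-up to the start of the Extended-Use phase; 7.1 and 7.2 do not.
- Protocol Appendix 6, on symptomatic deterioration: "Every effort should be made to document objective progression even after discontinuation of treatment". No schedule or data item supports this.

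**How it is analysed.** PFS and DOR events are progression or death from any cause. For subjects alive and free from progression at cutoff, lost to follow-up, "or discontinued from the study, or initiated subsequent anticancer therapy, PFS will be censored at the last adequate tumor assessment" (SAP 7.6.2). The DOR rule is the same. A subject with no evaluable post-baseline scan is censored for PFS at Day 1. SAP section 5 nevertheless keeps subjects with clinical progression before the first scan in the efficacy-evaluable set, and SAP 7.6 counts them as non-responders.

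**The concern.** Kaplan-Meier estimation assumes that a censored subject has the same outlook as those still followed. A subject taken off both drugs because of clinical decline probably does not. If no later disease status is recorded, that subject leaves the risk set as though progression-free, and the curve sits too high.

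The sharpest case lies inside the SAP: a subject with clinical progression before the first scan is a failure for ORR but contributes no event and no follow-up time to PFS unless a death is counted.

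PFS and DOR are named secondary endpoints in a nonrandomized trial. The protocol itself cites sotorasib monotherapy results (median PFS 6.3 months, median DOR 10 months), and readers will set the trial's estimates beside them.

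**Working it through.** The documents give no planned figure for PFS or DOR, so there is none to reproduce. The numbers below illustrate PFS only.

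**1. Tracing one subject.** The subject stops both drugs for clinical decline and the EOT scan does not meet RECIST progression. No scan is scheduled afterwards. The telephone call can yield a death or a new therapy.
- A death is an event, unless the SAP censors it because at least two consecutive scheduled scans were missed or new therapy came first. How the missed-scan rule works after EOT, when none are scheduled, is not stated. On the on-treatment schedule two scans span 12 weeks, or 24 weeks after Cycle 9.
- Without a counted death, the subject is censored at the last adequate scan, often the EOT scan itself.

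**2. Size, continuous dating of progression.**
- Inputs: true median 6.3 months, borrowed from the Phase 1 sotorasib result in Protocol 2.1.2; hazard ln 2 / 6.3 = 0.110 per month; scan spacing 42 / 30.4375 = 1.38 months. Assumptions: a share f of subjects stops for decline in the scan interval in which progression falls, and the EOT scan documents progression in a fraction q of them. The remaining f(1 − q) are censored at the preceding scan.
- Hand approximation: median ≈ 6.3 / [1 − f(1 − q)].

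| f | q | f(1 − q) | Approximation | Simulation |
|---|---|---|---|---|
| 15% | 0 | 0.15 | 6.3 / 0.85 = 7.4 | 7.3 |
| 15% | 50% | 0.075 | 6.3 / 0.925 = 6.8 | about 6.75 |
| 15% | 80% | 0.03 | 6.3 / 0.97 = 6.5 | 6.5 |

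The overstatement at f = 15% is therefore about 1.0, 0.5 and 0.2 months. With 46 subjects, 15% is 0.15 × 46 = 6.9 subjects.

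**3. Deaths.** With f = 15% and q = 0, if half of the affected subjects die about a month later and count as events, the simulated median is about 6.9 months. Deaths shrink the bias without removing it.

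**4. Scheduled dating of progression.** Scans fall every 6 weeks up to Cycle 9, which starts at week 24 (5.5 months), then every 12 weeks, so the next is at week 36 (8.3 months). True progression-free proportions are exp(−0.110 × 5.52) = 0.54 and exp(−0.110 × 8.28) = 0.40. If progression is dated only at these scans, the curve crosses 50% at 8.3 months. In simulation it stays there for every f from 0 to 20% with q = 0. The median is then insensitive because the curve has large steps.

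**5. Toxicity stops.** Let stopping occur at rate c = λf / (1 − f), with λ = 0.110, and let the progression hazard be rλ afterwards. True progression-free survival is

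S(t) = e^(−(λ+c)t) + c[e^(−rλt) − e^(−(λ+c)t)] / (λ + c − rλ).

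Censoring at the stop always gives a median of 6.3. At f = 14.8% the true median is 6.42 (r = 0.7), 6.30 (r = 1), 6.03 (r = 2) or 5.86 (r = 3). The sign depends on r, which the documents do not give.

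**The case against.** The strongest reply is that the plan already limits the problem. An EOT scan is required within 30 days of the last dose, when decline is likely to be visible. Deaths are events. If only RMC-4630 is stopped for toxicity, sotorasib may continue (Protocol 6.7), and imaging with it. Appendix 6 says that symptomatic deterioration does not describe an objective response, so leaving it out of the main PFS definition is legitimate. There is no hypothesis test, and with 46 subjects sampling error alone spreads a 6.3-month median from about 4 to over 9 months. SAP 7.6.2 also refers to a separate censoring-rule document for DOR (as 7.6.3 does for OS), which is not among the documents reviewed.

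Most of this stands and bounds the size. It does not remove the gap for subjects whose EOT scan falls short of RECIST progression, and a confidence interval reflects sampling error, not this bias.

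Four stronger readings are tempting and not supported:
- **That subjects are censored exactly when they stop treatment.** Stopping is not a listed censoring reason. Censoring falls at the last adequate scan.
- **That 15% is the expected share.** In CodeBreaK 101C, 4 of 27 subjects (15%) stopped one or both drugs for related adverse events. That is neither clinical decline nor necessarily the end of imaging.
- **That toxicity stops also inflate PFS.** Step 5 of the working shows that the direction is open.
- **That the mismatch is only a version gap.** The SAP is based on Protocol Version 4.0 and the protocol reviewed is Version 5.0. This may explain 7.1-7.2, but SAP 2.2.3 is inconsistent within itself.

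**Conclusion.** The inconsistency is established from the text: disease status is a stated purpose of LTFU in both documents, and neither schedules anything that would record it. The statistical consequence is conditional. For subjects who stop both drugs for clinical decline, without RECIST progression by the EOT scan and without a counted death, the censoring is potentially informative, with overstatement of PFS and DOR the expected direction.

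The size cannot be determined from the documents. The illustrative range for median PFS runs from no shift to about 1 month. It rests on an assumed exponential curve, an assumed 15% share and an assumed EOT detection rate. An unchanged median under scheduled dating would not show that the rest of the curve is unaffected. The same rule applies to DOR, for which no size is offered. ORR is unaffected because the PFS and DOR censoring rules do not enter it. The change is worth making as a low-cost safeguard for secondary endpoints, not as a correction to the primary analysis.

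**What to change.** 1. **SAP 7.6.2.** Add a PFS and DOR sensitivity analysis that counts treatment discontinuation for clinical progression or symptomatic deterioration as an event on the discontinuation date. Keep the RECIST-based analysis as the main one. First confirm that the eCRF discontinuation reason separates this category, since the list in Protocol 7.1 does not, and that the separate censoring-rule document agrees.
2. **Protocol 4.1.2 and SAP 2.2.3.** Reconcile them with Table 1, footnote 3 and Protocol 7.1-7.2. Either record, while main-study subjects are in LTFU, the date and basis of progression from local standard-of-care imaging and use it in PFS and DOR, or delete disease status from the stated purpose. Neither option adds a protocol scan. The sensitivity analysis is worth running under both.

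Cost: SAP wording, one additional table and, under the first option, one eCRF field. Local imaging off treatment will be less regular, and PFS may look slightly shorter.

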4.1.3. Duration of the Study

The main study duration is approximately 2 years. The Extended-Use phase will be conducted through June 2024.

4.1.4. Intervention After the End of the Study

Subjects who are on treatment at the EOS and are deriving clinical benefit from RMC-4630 and sotorasib may be considered for enrollment in a separate Extended-Use phase of the study. These subjects should enter the separate Extended-Use phase without interruption of treatment and should complete EOT assessments listed in the SoA ([Table 1](#)) prior to treatment on Day 1 of the Extended-Use phase. Assessments outlined in the SoA are to be followed during the Extended-Use phase of the study.

4.2. Scientific Rationale for Study Design

This is a Phase 2 study designed to characterize the efficacy, safety, tolerability, and PK of RMC-4630 and sotorasib combination therapy in subjects with *KRAS^{G12C}* mutant locally advanced or metastatic NSCLC after failure of prior standard therapy. The PK (trough and approximate peak concentrations) and efficacy (ORR, DOR, and PFS assessed per RECIST v1.1) endpoints in this study are commonly used for PK modeling and characterization of exposure/safety and exposure/efficacy relationships for the target population of subjects with *KRAS^{G12C}* mutant NSCLC.

4.3. Dose Justification

4.3.1. RMC-4630

RMC-4630 is being studied in the clinic as a monotherapy in Study RMC-4630-01 (NCT03634982), and in various other combination studies. RMC-4630 has been tested at various dose levels and schedules including daily dosing, intermittent dosing schedule on [REDACTED] and [REDACTED]. As of 16 November 2020, [REDACTED] have been treated with RMC-4630

monotherapy; the RP2DS was determined to be [REDACTED] of each week in a 21-day cycle. At this dose level, the plasma concentrations of RMC-4630 were above those predicted to be clinically active, based on preclinical models. The C_{max} reached, and often exceeded, the apoptotic threshold (75% effective concentration [EC₇₅]), defined as plasma concentrations that were associated with induction of tumor regressions or cell death in preclinical models. Trough concentrations at the end of each week were close to the 50% effective concentration (EC₅₀) for RAS signaling pathway inhibition in tumors, which was predicted to be sufficient to permit normal tissue recovery and therefore contribute to tolerability.

Furthermore, RMC-4630 and sotorasib combination is being tested in an ongoing Amgen-sponsored Phase 1b platform (CodeBreaK 101C). CodeBreaK 101C was initiated in May

2020 and is currently dosing subjects at RMC-4630 [REDACTED]

[REDACTED] of each week in a 21-day cycle and [REDACTED] of each week in a 21-day cycle). This Phase 2 study (RMC-4630-03) will have a safety run-in period in which RMC-4630 will be administered at [REDACTED] of each week in a 21-day cycle as the starting dose with the option of escalating to RMC-4630 [REDACTED] of each week in a 21-day cycle if tolerated per modified toxicity probability interval 2 (m-TPI2).

